## OUTCOME MEASUREMENTS

The primary outcome was the rate of postoperative UTI within 6 weeks after surgery. The Center for Disease Control and Prevention's definition of a symptomatic UTI was adapted to include the following: (1) at least one sign or symptom accompanied by positive urine culture with  $\geq 105$  colony-forming units/ml, (2) symptomatic UTI with clinician decision to treat as reported by the patient, or (3) at least one sign or symptom with positive urine dipstick (UA). Timing of diagnosis was recorded as either the date of the positive urine culture or the timing of the postoperative phone call when the patient reported treatment of a UTI (3 days, 2 weeks, or 4 weeks after surgery). A sensitivity analysis was performed of UTIs treated within 2 weeks of surgery and any adverse effects related to the use of antibiotic irrigation. We also evaluated outcomes in the subgroup who had a vaginal prolapse repair procedure, which was previously reported to be at highest risk for postoperative UTI.

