## STUDY PROTOCOL

At the time of surgery, the randomization allocation envelope was opened by the surgical fellow. If indicated, this individual prepared the antibiotic solution by injecting 1 ml of neomycin or polymyxin into 1 L normal saline. The fellow remained independent of postoperative UTI diagnosis and treatment for study participants. The steps of the surgery remained standard; the study protocol made no alterations to usual care involving patient preparation, intravenous antibiotics, and instrumentation. We routinely use cefazolin for antibiotic prophylaxis for all surgeries, with the addition of metronidazole for hysterectomy in premenopausal patients, except in the case of associated allergies. Upon routine urinary catheter insertion, a urine sample was collected and sent for culture. Patients with a positive intraoperative urine culture were later excluded from analysis.

Intraoperative cystoscopy was performed in normal fashion with the previously designated bag of irrigation fluid. At the completion of cystoscopy, the bladder was drained as per standard operating procedure. To determine the volume of fluid used during cystoscopy, the fluid bag was weighed before surgery and again after cystoscopy. A foley catheter was replaced per surgeon discretion. Upon hospital discharge, standardized post-operative instructions were given to all patients, including signs and symptoms of infections or other concerning postoperative sequelae.

Postoperatively, patients were called at three time points (3 days, 2 weeks, and 4 weeks after surgery) to assess for urinary complaints and adverse events, including patient-reported diagnosis and treatment of UTI. Subjects were treated for postoperative UTI per attending surgeon discretion.

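### The primary outcome runs to 6 weeks, but the last described contact is the 4-week call, so UTIs known only by patient report have no described active capture in weeks 4 to 6

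*Combined protocol and SAP*

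**What the plan says.** The document is a combined protocol and SAP. Three statements bear on this point.

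- **Window.** Outcome Measurements: "The primary outcome was the rate of postoperative UTI within 6 weeks after surgery".
- **Contacts.** Study Protocol: "patients were called at three time points (3 days, 2 weeks, and 4 weeks after surgery"), and their purpose was "to assess for urinary complaints and adverse events, including patient-reported diagnosis and treatment of UTI".
- **Dating.** Outcome Measurements: "Timing of diagnosis was recorded as either the date of the positive urine culture or the timing of the postoperative phone call". The call meant is the one at which a woman said she had been treated, and the section lists the same three times for it, the latest being 4 weeks.

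A UTI could qualify in three ways: (1) a sign or symptom with a positive culture; (2) "symptomatic UTI with clinician decision to treat as reported by the patient"; or (3) a sign or symptom with a positive dipstick. Only criterion (2) is defined by what the patient reports.

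Two further statements describe care outside the calls. Study Protocol says "Subjects were treated for postoperative UTI per attending surgeon discretion", and that discharge instructions covered signs of infection. The Intervention, Randomization, and Blinding section says that the attending surgeon assessed and treated postoperative UTIs and that this surgeon and the patients stayed blinded.

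**The concern.** The scheduled contacts do not cover the outcome window. The calls are the described means of learning about UTIs that patients report, and they stop two weeks before the window closes. The dating rule stops at the same place.

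A woman who is UTI-free at the 4-week call and is then treated on symptoms alone, with no qualifying culture or dipstick, meets the definition of the primary outcome. The plan describes no step at which she would be asked about it.

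What is at stake is the completeness of the primary endpoint. The plan does not say what was done to find events after week 4, or how women with no later contact were classified. A reader cannot tell whether the reported figure is a full 6-week rate, or a 4-week rate plus whatever late events came to the site's notice.

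**Working it through.** The plan gives no figure to reproduce here. The check sets the rules side by side, and then asks what can be said about the direction of any effect.

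**Step 1: coverage of the window.** The window is 6 × 7 = 42 days (Outcome Measurements). The last call is at 4 × 7 = 28 days (Study Protocol). Days after the last call: 42 − 28 = 14, and 14/42 = 33%. This is a share of time, not of events; the documents do not give the timing of UTIs.

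**Step 2: capture and dating in weeks 4 to 6, by criterion.**

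| Criterion | Described active capture | Other route |
|---|---|---|
| (1) culture | none | culture, if the woman presents; dated by the culture |
| (2) patient-reported treatment | none; last call is at 4 weeks | surgeon's care, but no transfer to the study data is described |
| (3) dipstick | none | dipstick, if the woman presents |

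The exposed group is therefore narrow: mainly women whose only qualifying event is a criterion (2) UTI in weeks 4 to 6. Two separate sentences, on the calls and on the dating of reports, both end at 4 weeks, so a single dropped word is an unlikely explanation.

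**Step 3: can the effect on the comparison be signed?** Inputs from Statistical Analysis: a 20.3% UTI rate, whose time window is not stated, and 186 women before the dropout allowance. 186 × 1.30 = 241.8, which matches the stated 242 in total, so 186 is a total and each arm has 186/2 = 93. Assumption: the planned 50% reduction is read as relative, giving 0.203 × 0.5 = 10.15% with antibiotic. The difference is then 10.15 points and the risk ratio 0.50.

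Power = Φ[(d − 1.96 × SE0)/SE1], where d = p1 − p2, SE0 = √(2p̄(1 − p̄)/93) with p̄ the mean of p1 and p2, and SE1 = √([p1(1 − p1) + p2(1 − p2)]/93). With nothing missed, power is 48.7%. That low starting value comes from the sample-size calculation, which is a separate matter.

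Two patterns of loss, both assumed:

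- *Same proportion lost in each arm*, for example 5% of events: 0.203 × 0.95 = 19.29% and 0.1015 × 0.95 = 9.64%. Difference 9.64 points, ratio 0.50, power 46.4%.
- *Same number of points lost in each arm*. One point: 19.3% and 9.15%; difference 10.15 points, ratio 9.15/19.3 = 0.47, power 50.9%. Two points: 18.3% and 8.15%; difference 10.15 points, ratio 8.15/18.3 = 0.45, power 53.4%.

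Under the first pattern the difference and power fall and the ratio holds. Under the second the difference holds, the ratio moves away from 1 and power rises. The event rate falls in both arms under either pattern. The loss sizes are chosen only to show direction; they are not estimates of what was missed.

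**The case against.** The strongest case against is that an outcome window and a call schedule may differ without contradiction. The plan nowhere says that the calls were the only means of ascertainment. This was a single center, the attending surgeon handled postoperative UTIs, and every woman went home with instructions on signs of infection. On this view a detail of ascertainment is unreported and nothing more. Part of this stands: there is a passive route, and it is wrong to say that two rules contradict each other. But the sentence about the surgeon's role is there to describe blinding, and the plan does not say how events known to the surgeon reached the study data. Followed as written, the schedule can miss events that count toward the primary endpoint.

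It is also fair that the missing time label matters little in itself. The analysis compares rates by chi-square and logistic regression, with no time-to-event method, so the label matters only for placing an event inside or outside the window. And the planned sensitivity analysis of UTIs treated within 2 weeks lies wholly inside the period covered by calls, so it does not depend on capture after week 4.

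Three stronger readings might be inferred, and the documents support none of them:

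- *That no UTI could be counted after week 4.* Cultures carry their own date, and dipsticks can be done whenever a woman presents.
- *That the gap biases the comparison between arms.* Patients and the attending surgeon were blinded, and the fellow who opened the envelope had no part in diagnosing or treating UTIs.
- *That the gap shrinks the risk difference or costs power.* This follows from equal proportional loss. The intervention is a single intraoperative irrigation, so similar absolute late rates in both arms are just as open an assumption, and they give the opposite result for power.

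**Conclusion.** The point holds as a minor one. The described contacts end at day 28 of a 42-day primary window, and UTIs that qualify only by patient report have no described active capture in the last 14 days. Confidence in that is high, because it rests on the text alone.

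The consequence is limited to a possible undercount of the 6-week rate. Its size is unknown: the documents give neither the timing of UTIs nor their split by criterion. The absence of evident between-arm bias rests on the stated blinding. If a postoperative visit or chart review did cover weeks 4 to 6, saying so would settle the question of capture.

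**What to change.** **At design.** Keep the 4-week call and add a short call at 6 weeks, so that the last contact falls at the end of the outcome window. Record the treatment-start date for any UTI reported. Cost: one extra short call per woman and one date field.

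**After follow-up** (the Design, Setting, and Participants section gives September 2019 as the end of the study):

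- keep UTI within 6 weeks as the primary outcome;
- add a sensitivity analysis of UTI within 4 weeks, labelled as such, which matches the last call;
- report the week 4 to 6 events by arm and by criterion;
- state what ascertainment was done after week 4.

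Cost: one extra analysis, one small table and a short addition to the methods. The primary endpoint is unchanged and no events are discarded. These steps cannot recover events that were never reported, but they let a reader judge how far the result depends on the uncovered fortnight.

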## Study Protocol and Statistical Analysis

### MATERIALS AND METHODS

This was an investigator-initiated double-blind randomized controlled trial approved by the Institutional Review Board at MetroHealth Medical Center in Cleveland, OH and registered with clinicaltrials.gov (CT03099863). We conducted and reported this study according to the consolidated standards of reporting trials guidelines for randomized controlled trials. An independent data safety monitoring committee oversaw this trial. We had no extra-institutional funding.

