### INTERVENTION, RANDOMIZATION, AND BLINDING

Patients were randomized 1:1 at the time of surgery into two groups based on the type irrigation to be used with intraoperative cystoscopy: control (normal saline) or antibiotic (Neosporin G.U. [200,000 U polymyxin B sulfate +40 mg neomycin sulfate] in 1 L NS). The randomization scheme was assigned by a statistician using randomization software in blocks of 10. Allocation was concealed in an opaque envelope until the time of randomization. The patients and attending surgeon, who performed all evaluation and treatment of postoperative UTIs, remained blinded. Neosporin G.U. (Pfizer, 200,000 U polymyxin B sulfate 40 mg neomycin sulfate) is Food and Drug Administration approved for short-term use as a bladder irrigant to prevent bacteriuria associated with the use of indwelling catheters. The prepared solution is completely clear, bactericidal, and used as indicated, neomycin and polymyxin B are absorbed in clinically insignificant quantities. A neomycin or polymyxin solution was used in Hares' 1981 cystoscopy irrigation study, has been used successfully in spinal cord injury patients with bacteriuria, and is well tolerated. Additionally, the medication is inexpensive and readily available in our operating room pyxis.

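### The safety outcome is defined by relatedness to the antibiotic, with no assessor or causality rule, and so makes no use of the blinded saline arm

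*Combined protocol and SAP*

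**What the plan says.** The safety outcome appears once, in the second half of a sentence in Outcome Measurements: "A sensitivity analysis was performed of UTIs treated within 2 weeks of surgery and any adverse effects related to the use of antibiotic irrigation". The safety item itself is "any adverse effects related to the use of antibiotic irrigation". The plan gives no event list, grading, causality rule or named assessor, and no test specific to adverse events.

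Collection is described in Study Protocol. Women were telephoned on three occasions (day 3, week 2 and week 4) "to assess for urinary complaints and adverse events, including patient-reported diagnosis and treatment of UTI". Nothing there restricts the question to one arm or to events thought to be caused by the irrigant.

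On blinding, the Intervention, Randomization, and Blinding section says: "The patients and attending surgeon, who performed all evaluation and treatment of postoperative UTIs, remained blinded". Study Protocol says that "the randomization allocation envelope was opened by the surgical fellow", who also mixed the antibiotic solution where it was allocated, and adds: "The fellow remained independent of postoperative UTI diagnosis and treatment for study participants". On oversight, Materials and Methods says: "An independent data safety monitoring committee oversaw this trial". No section says who made the calls or who decided whether an event was related.

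Statistical Analysis contains one general statement that the randomised groups were compared by a chi-square test for categorical data. It does not mention adverse events.

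**The concern.** Urinary symptoms and other complaints are to be expected after pelvic surgery with catheterisation and cystoscopy, whichever fluid is used. A blinded saline arm measures that background. An event count restricted to effects of the antibiotic sets the background aside and puts a case-by-case opinion in its place.

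The error could go either way. Background events in antibiotic-arm women may be called related, which overstates harm. True irritation from the irrigant may be put down to the operation, which hides harm. In both cases a statement on tolerability would rest on an undescribed attribution step and not on the randomised comparison.

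**Working it through.** The plan states no adverse event rate, safety margin or safety sample size, so there is no figure of its own to reproduce. The check sets the sections side by side and then follows the definition through.

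**Step 1. What is collected against what is analysed.**

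| Item | Collection (Study Protocol) | Outcome (Outcome Measurements) |
|---|---|---|
| Arms covered | No restriction | Literally, the antibiotic arm only |
| Relatedness filter | None | Related to the antibiotic irrigation |
| Who decides relatedness | Not needed | Not stated |
| Rule for deciding | Not needed | Not stated |

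**Step 2. What each definition estimates.** Let *b* be the background probability of an adverse event, *d* the increase caused by the antibiotic, and *q* the proportion of antibiotic-arm events that an assessor calls related.

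- Outcome as worded: antibiotic arm (*b* + *d*) × *q*; saline arm 0 by definition. Difference = (*b* + *d*) × *q*.
- All events by arm: antibiotic arm *b* + *d*; saline arm *b*. Difference = *d*.

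If the antibiotic does nothing (*d* = 0), the worded outcome still shows a difference of *b* × *q*, which is above zero whenever any background event is called related. If the antibiotic does harm (*d* > 0) but no event is called related (*q* = 0), the worded outcome shows nothing. The all-event difference is *d* in both cases and does not depend on *q*.

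**Step 3. Does the general chi-square statement repair this?** Applied to the outcome as worded, it compares the antibiotic count with a structural zero, so it tests (*b* + *d*) × *q* = 0 and not *d* = 0. It would be a suitable test for the all-event table, but the plan does not say that such a table is to be made.

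**Step 4. Who could make the attribution?** The blinding and independence statements for the surgeon and the fellow refer to evaluating, diagnosing and treating UTI. Neither person is assigned adverse event causality. The monitoring committee is not given that task either. The role is unassigned.

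**Step 5. How much could an all-event comparison show?** This step rests on assumed control rates of 1%, 5% and 10%, because the documents give none. For *n* per arm and two-sided alpha 0.05, with rates *p*1 and *p*2 and mean rate *p*:

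power = Φ( [ |*p*2 − *p*1| × √*n* − 1.96 × √(2*p*(1 − *p*)) ] / √(*p*1(1 − *p*1) + *p*2(1 − *p*2)) )

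For 5% against 10% with *n* = 121: (0.05 × 11 − 1.96 × √0.13875) / √0.1375 = (0.550 − 0.730) / 0.371 = −0.486, and Φ(−0.486) = 0.31.

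| Assumed doubling | 121 per arm (planned enrolment) | 93 per arm (186 / 2) |
|---|---|---|
| 1% to 2% | 9% | 8% |
| 5% to 10% | 31% | 25% |
| 10% to 20% | 59% | 48% |

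So the all-event comparison removes the dependence on attribution, but it would be imprecise. It should be read as an estimate with a confidence interval, and a non-significant result should not be taken as evidence of safety.

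**The case against.** The strongest reply is that one loose clause is being read at its most literal. The phrase may mean only that adverse events were examined in relation to antibiotic use, which would itself be a comparison of exposed with unexposed women. The documents do not say that events were attributed one by one or that saline-arm events were set aside. The calls are unfiltered, the patients are blinded, and the general chi-square statement could be applied to all events. The plan also describes the irrigant as already approved, little absorbed and well tolerated, and there was independent safety oversight.

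Much of this limits the point without removing it. The looser reading is possible, but it is not the ordinary sense of the words, and if it was meant the fix states it plainly. Independent oversight and prior tolerability do not define an outcome.

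Two stronger conclusions that a reader might draw are not supported:

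- **That the trial can give no valid between-arm safety comparison.** This is true of the outcome as worded. It is not true of the data, because the calls cover both arms without a relatedness filter.
- **That the blinded surgeon had to make an attribution that blinding ruled out.** No section gives the surgeon that task. An assessor blind to arm can judge whether an event is related to the irrigation in either arm, so blinding does not prevent a relatedness judgement. What the documents support is that the assessor is not named. The fellow, who knew the allocation, is declared independent only for UTI, so the text does not exclude a part in adverse event attribution. Nor does it show one.

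The label of sensitivity analysis is also loose for what is a separate outcome, but changing the label alone would change no analysis.

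**Conclusion.** The concern holds as a defect in how the safety outcome is defined. It depends on an exposure that the control arm never had, names no assessor or causality rule, and does not match the unfiltered collection at the three calls. As worded, it leaves the blinded control arm unused for safety.

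The control count is zero by construction on the literal reading. Beyond that no size can be given, because both the background event rate and the share of events called related are absent from the documents. The primary outcome, its test and its sample size are untouched. The conclusion rests on the ordinary reading of the clause and on the calls having been made as described in both arms. The change is worth making because it replaces an opinion-based count with a randomised comparison from data the protocol already collects.

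**What to change.** Define the safety outcome as all adverse events reported at the three scheduled calls, in both arms, regardless of judged relatedness. Compare the proportion of women with any event, and with each event type, by randomised arm, and give the difference with a confidence interval. State the denominator used.

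If relatedness is also reported, have it judged by someone blind to arm, in both arms, as relatedness to the study irrigation whichever fluid was used. Name the assessor's role and the rule. List the item as a safety outcome in its own right.

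The cost is a change of wording and one table from information the calls were meant to gather, provided the call records allow events to be classified by type. The drawback is that the table will include many ordinary postoperative events, so it will be longer and noisier than a list of suspected drug effects.

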## STATISTICAL ANALYSIS

Based on 20.3% incidence of postoperative UTI, we determined that a sample size of 186 would provide 80% power to detect a 50% absolute reduction in postoperative UTI rates at a two-sided  $\alpha = .05$ . To account for an estimated 30% dropout rate with positive intraoperative urine culture or loss to follow up, we adjusted the total sample size to 242 patients total, with 121 subjects in each study arm.

Data was collected in our institutional REDCap database, and statistical analysis was performed with Stata version 15.1 (StataCorp). Covariates included in the analysis were patient-specific characteristics and medical comorbidities (age, race, obesity, smoking status, menopausal status, and history of Type 2 diabetes, recurrent UTIs, thyroid disease, asthma, hypertension, reflux disease, depression, or anxiety) and volume of cystoscopy fluid used. Surgeries were characterized as primary vaginal or laparoscopic, and all concurrent procedures were noted. The randomized groups were compared using Pearson's  $\chi^2$  test for categorical variables and the Student's t test for normally distributed continuous variables. Multivariable logistic regression analysis was used to adjust for possible confounding variables impacting the effect of antibiotic irrigation on postoperative UTI rates. Covariates significant on univariate analysis with  $p < .2$  or with notable clinical relevance were included in the logistic regression. All results yielding  $p < .05$  were deemed statistically significant.

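### The total of 242 does not cover the plan's own 30% loss: it leaves about 169 evaluable women, not the 186 required

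*Combined protocol and SAP*

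**What the plan says.** The sample size paragraph of the Statistical Analysis section has two steps.

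- **Base size.** The starting rate is given as "Based on 20.3% incidence of postoperative UTI". From this, "we determined that a sample size of 186 would provide 80% power". The effect that this power refers to is worded as "to detect a 50% absolute reduction in postoperative UTI rates", and the significance level is 5%, two-sided.
- **Allowance for loss.** The plan expects 30% of women to be lost, either because the culture taken during surgery is positive or because follow-up is incomplete. The outcome of the allowance is reported as "we adjusted the total sample size to 242 patients total, with 121 subjects in each study arm".

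The second step turns 186 into a total of 242, so the plan treats 186 as a total, or 93 per arm. It does not give the inflation formula.

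Two other sections show which women the 30% applies to. Under Intervention, Randomization, and Blinding, women are allocated 1:1 at surgery. Under Study Protocol, the urine sample is taken when the catheter is inserted, and women whose culture proves positive are removed from the analysis afterwards.

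**The concern.** An allowance for loss exists so that the required number remains once the expected losses have occurred. If a fraction d of those randomised is lost, the number to randomise is n / (1 − d). Multiplying by (1 + d) gives a smaller number, and the gap widens as d grows. At 30% it is no longer negligible.

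The paragraph tells the reader that 242 randomised women protect 80% power against a 30% loss. If they do not, the trial was planned to fall short of its own requirement whenever its own loss assumption held. Anyone weighing a null result against the stated power would be relying on a number of evaluable women that the plan did not secure.

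**Working it through.** **Inputs**

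| Input | Value | Source |
|---|---|---|
| Evaluable women required | 186 (93 per arm) | Statistical Analysis |
| Expected loss | 30% | Statistical Analysis |
| Total to randomise | 242 (121 per arm) | Statistical Analysis |
| Control rate | 20.3% | Statistical Analysis |
| Significance level | 0.05, two-sided | Statistical Analysis |
| Allocation | 1:1 | Intervention, Randomization, and Blinding |

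**Step 1: reproduce 242.**
- n × (1 + d): 186 × 1.3 = 241.8, rounded up to 242. Per arm, 93 × 1.3 = 120.9, rounded up to 121. Both stated figures match.
- n / (1 − d): 186 / 0.70 = 265.7, rounded up to 266 (133 per arm). This does not match.

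**Step 2: apply the stated loss to the stated total.**
- 242 × (1 − 0.30) = 169.4 evaluable, or 84.7 per arm.
- Shortfall: 186 − 169.4 = 16.6, about 17 women; 16.6 / 186 = 8.9%.

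This step does not depend on how 242 was reached.

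**Step 3: find the loss that 242 does cover.**
- 1 − 186 / 242 = 56 / 242 = 23.1%.

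**Step 4: the cost in power.** The usual normal approximation with pooled variance under the null, for n per arm, is

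power = Φ{ [ |p₁ − p₂| √n − 1.96 √(2p̄(1 − p̄)) ] / √(p₁(1 − p₁) + p₂(1 − p₂)) }, with p̄ = (p₁ + p₂)/2.

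The plan's effect cannot be used literally, because a fall of 50 percentage points from 20.3% is impossible. Two effects are therefore shown. The first reads the 50% as relative, which is an assumption: 20.3% to 10.15%. The second is back-solved so that 93 per arm gives exactly 80% power: 20.3% to about 6.4%. The 6.4% appears nowhere in the plan and serves only to isolate the effect of the loss step.

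| Effect | 93 per arm (186) | 84.7 per arm (169.4) | Change |
|---|---|---|---|
| 20.3% vs 10.15% | 48.7% | 45.1% | −3.6 points |
| 20.3% vs 6.4% | 80.0% | 76.2% | −3.8 points |

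For the first row at 93 per arm: p̄ = 0.15225, and the numerator is 0.1015 × 9.644 − 1.96 × 0.5081 = −0.017. Dividing by 0.503 gives −0.034, and Φ(−0.034) = 0.487. At 84.7 per arm the numerator is 0.1015 × 9.203 − 1.96 × 0.5081 = −0.062. Dividing by 0.503 gives −0.123, and Φ(−0.123) = 0.451.

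**The case against.** Four points can be made for the plan.

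- **The formula is inferred.** The plan never says that it multiplied by 1.3. This is correct. The match in both the total and the per-arm figure makes the inference strong, but it remains an inference. The shortfall in Step 2 does not need it.
- **The 30% might be an addition to 186 rather than a loss from 242.** On that reading 242 is consistent, since 56 / 186 = 30.1%. But the text calls it "an estimated 30% dropout rate with positive intraoperative urine culture or loss to follow up", and a dropout rate is normally a share of those who enter. Both named causes remove women from the analysis after allocation, so they come out of the 242.
- **The effect is small, and a larger problem sits beside it.** This stands as a matter of weight. The loss step costs about 4 points of power. The base figure costs far more: for 20.3% vs 10.15%, the same method gives 196 per arm (392 in total) for 80% power, against 186 in total. Having 186 evaluable women would therefore still leave about 49% power for a halving. The two errors are independent, and repairing one does not repair the other.
- **Enrolment is over.** The document describes a trial run from May 2016 to September 2019, so the target cannot now be changed. The shortfall also arises only if the loss really was 30%. If 23.1% or fewer were lost from 242, 186 was reached. The documents do not give the actual number. This limits the remedy to the text, but the paragraph still claims a protection that 242 does not provide.

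**Conclusion.** The concern holds. At the plan's own 30% loss, 242 randomised women leave about 169 evaluable, 17 fewer (9%) than the stated requirement, and 242 is sufficient only up to a 23.1% loss. The consequence for power is about 4 percentage points.

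The conclusion on numbers rests on two readings, both supported by the text: that 186 is a total, and that the 30% is a share of those randomised. The power figures rest additionally on the assumed effects (a relative halving, or the back-solved 6.4%) and on the normal approximation. This is a real but moderate error, secondary to the question of whether 186 was the right base.

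**What to change.** Correct the sentence on the loss allowance in the Statistical Analysis section in one of two ways:

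- state that 242 women randomised, with 30% lost or excluded, leave about 169 evaluable (about 85 per arm), and give the power at that number for an effect written as two rates (for example, about 45% for 20.3% vs 10.15%, if a halving was meant); or
- state that 242 preserves 186 evaluable women only if no more than 23% are lost or excluded.

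In either case, state the inflation formula and that the percentage refers to women randomised. Because recruitment has ended, no change to enrolment is proposed. The corrected division, giving 266, shows the size of the error; it would not have given 80% power for a halving.

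The cost is one sentence, with a less favourable evaluable number and power. No treatment, endpoint or analysis changes.
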